8.0 REGULATORY AND REPORTING REQUIREMENTS

Subjects will be monitored for adverse events during the actual imaging period. Since FDG-PET/CT imaging is provided per standard of care no adverse event assessments will be recorded. For FFNP-PET/CT imagings, subjects will be contacted by phone or in person approximately

24± 6 hours after the injection of ¹⁸F-FNP to assess for adverse events as related to ¹⁸F-FNP injection, or PET/CT imaging. Any adverse events that occur within 24 hours of administration of ¹⁸F-FNP or within 24 hours of the first dose of estradiol which are graded related or possibly related to participation in the research will be reported according to the guidelines below:

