5.2 Patient Population

Fifty postmenopausal women OR Pre-menopausal for whom standard ET is planned with ovarian suppression (imaging on study should be completed prior to start of ovarian suppression) with newly diagnosed, metastatic or recurrent breast cancer which is ER+ disease (ER+/PgR+/HER2-, ER+/PgR-/HER2-) will undergo one FDG PET/CT scan to map the metabolically active disease plus two ^{18}F -FFNP-PET/CT; one prior to estradiol challenge test and a second one immediately following one day of estradiol challenge test (2 mg tid). All scans will be completed prior to the start of standard of care ET. Patients who have had an FDG-PET/CT scan (or other functional studies such as bone scan in patients with bone dominant disease or a contrast CT scan for hepatic dominant disease) done within 8 weeks of study entry may not need to repeat the scan at the discretion of the Principal Investigator and Co-Investigator Medical oncologists. Any subject whose imaging is deemed not evaluable for any reason or any subject who does not complete both FFNP-PET/CT imaging sessions for any reason may be replaced on study. The study ID assigned to the subject being replaced will not be re-used.

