6.0 IMAGING PARAMETERS AND ANALYSIS

All research imaging studies will be performed using the CTI/Siemens Biograph 40 PET/CT scanner. The Biograph 40 is a 4-ring PET scanner made up of a multi-LSO-detector ring system with 3D acquisition and reconstruction and 109 image planes with an extended 21.6 cm axial field of view, enabling the detection of 78% more photons (compared with a conventional-field-of-view scanner). The scanner features high resolution (less than 5mm in transaxial and axial dimensions) with Pico 3D ultra-fast electronic for decreased dead-time and high signal-to-noise ratio.

All patients will undergo routine clinical staging as dictated by the treating medical oncologist or surgeon. The results of the PET studies will not be provided to the patient or the treating oncologist unless the CT images demonstrate an unsuspected, potentially life-threatening abnormality that warrants further investigation and/or urgent therapy (e.g., a mass impinging on the spinal cord seen on the CT images).

If performed for research purposes, the results of the ^{18}F -FDG-PET/CT scan will be fully interpreted and reported to the medical record following the same procedures as if done as a standard of care examination.

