6.1 Drug Preparation

6.1.1 ^{18}F -FFNP

^{18}F -FFNP will be prepared using an adaptation of a published procedure (Buckman BO J Med Chem. 1995;38(2):328-37; Kym PR J Med Chem. 1993;36(9):1111-9 ; Vijaykumar D J Org Chem. 2002;67(14):4904-10) . The diastereomerically pure 21-mesylate, endo-9a precursor was reacted with non-resin-treated [^{18}F]-fluoride, Kryptofix222 (Aldrich), and potassium carbonate in acetonitrile at 85C for 5 min. The reaction mixture was prepurified by passing through a silica light SepPak (Waters), followed by reversed-phase high-performance liquid chromatography purification. ^{18}F -FFNP was extracted from the high-performance liquid chromatography mobile phase using solid-phase extraction and was reconstituted in 10% ethanol in saline. Starting from 11.1 GBq (300 mCi) of ^{18}F fluoride and using 0.4 mg of potassium carbonate and prompt work-up to avoid the decomposition of the acid- and base-labile ^{18}F -FFNP, we

produced 0.74–1.11 GBq (20–30 mCi) of ^{18}F -FFNP at the end of synthesis (90 min). The final formulation of ^{18}F -FFNP is stabilized in ethanol or saline. Non-resin-treated ^{18}F -fluoride was used to achieve high specific activity. The specific activity was measured by high-performance liquid chromatography to be 185–740 GBq (5,000–20,000 mCi)/ μmol , and the effective specific activity was measured by receptor binding assay to be up to 740 GBq (20,000 mCi)/ μmol .

6.1.2 ^{18}F -FDG

FDG will be prepared and distributed under the Washington University Cyclotron Facility's ANDA for FDG.

6.2 ^{18}F -FDG-PET/CT Imaging Parameters

If performed for research purposes, subjects will undergo standard oncologic ^{18}F -FDG-PET/CT imaging that includes the base of the skull to upper thighs (or extended to include metastatic disease in the lower legs, or possible brain metastasis, if applicable) imaging.

Subjects will be asked to fast for a minimum of 4 hours with only plain water to drink during the fasting period. On the day of the scheduled scan a small IV catheter will be placed in an upper extremity arm vein (preferably contralateral to the patient's breast cancer) to allow for injection of FDG. Prior to injection a small sample of blood (less than 1 teaspoon) will be obtained for glucose measurement. Injection of FDG will proceed if blood glucose, if 200 mg/dL or less or with approval of the PI or nuclear medicine co-investigator (authorized user), if blood glucose is greater than 200 mg/dL.

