
6.6 Toxicities Related to ^{18}F -FDG & ^{18}F -FFNP PET/CT Imaging

Likely:

- Mild discomfort from the placement of the IV in the patient's arm.

Less Likely:

- Discomfort from lying still on the imaging table.
- There is a slight risk of bruising at sites of vein puncture.

Rare:

- There is a remote risk of infection and an even smaller risk of blood clot at the site of the IV placement
- There is a rare possibility of an allergic-type or other adverse reaction to radioactively labeled drugs. While none have been reported to date with the

radioactive materials ^{18}F -FFNP or ^{18}F -FDG, such a reaction could be serious and may result in death.

- **RADIATION EXPOSURE FROM PET/CT IMAGING:** the amount of radiation exposure the patient will receive from one injection (15mCi) of ^{18}F -FDG and the CT scan for attenuation correction is equivalent to a uniform whole body exposure of approximately 1.51 rem. The amount of radiation exposure from ^{18}F -FFNP injection and the CT scan for attenuation correction is equivalent to a uniform whole body exposure of approximately 1.39 rem. Patients will be scanned on 2 separate occasions with FFNP plus one FDG scan resulting in a total exposure of 4.28 rem.

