6.9 FOLLOW UP PROCEDURES

Follow up will consist of 2 parts. To assess for adverse events, approximately 24 ± 6 hours following injection, a follow-up telephone call will be made to the patient, or if the patient chooses another family member who will be able to assess for adverse events. In the event the patient is scheduled to be at the hospital for other testing or appointments, the assessment can also be made in person

Clinical follow-up via chart review will occur to document clinical progression of disease or change in therapy. Follow up chart review to assess for overall treatment response will also be conducted. A chart review will be conducted periodically until recurrence, progression or change in treatment. Data collected from the chart will include office notes from treating physicians, laboratory test results used to determine overall response and radiology reports and images. Response will be determined by the treating physician(s)

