8.1 Adverse Events (AEs)

Definition: any unfavorable medical occurrence in a human subject who receives ¹⁸F-FNP-PET/CT and / or estradiol as part of the estradiol challenge for research purposes only, including any abnormal sign, symptom, or disease. The event does not necessarily have to be causally related to injection of ¹⁸F-FNP or PET/CT imaging to qualify as an adverse event, just temporally related.

Grading: The descriptions and grading scales found in the revised NCI Common Terminology Criteria for Adverse Events (CTCAE) version 4.0 will be utilized for all toxicity reporting. A copy of the CTCAE version 4.0 can be downloaded from the CTEP website.

Attribution (relatedness), Expectedness, and Seriousness: the definitions for the terms listed that should be used are those provided by the Department of Health and Human Services' Office for Human Research Protections (OHRP). A copy of this guidance can be found on OHRP's website: (<http://www.hhs.gov/ohrp/policy/AdvEvtGuid.htm>).

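### Section 8.0 waives adverse event recording for every FDG scan as standard of care, although the protocol provides for FDG scans done for research

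*Combined protocol and SAP*

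**What the plan says.** Section 8.0 opens by saying that subjects are monitored for adverse events during imaging. It then makes an exception: "Since FDG-PET/CT imaging is provided per standard of care no adverse event assessments will be recorded". Contact at about 24 ± 6 hours is tied to FFNP, and the reportable windows are 24 hours from FFNP and 24 hours from the first estradiol dose. FDG has no window.

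Section 8.1 defines an adverse event by reference to a subject who receives FFNP-PET/CT and/or "estradiol as part of the estradiol challenge for research purposes only". FDG is not named.

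Elsewhere the protocol treats FDG as a possible study procedure:

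- Section 5.2 includes one FDG scan for each patient. Those with a suitable functional study in the 8 weeks before entry "may not need to repeat the scan at the discretion of the Principal Investigator" and the co-investigator oncologists.
- Section 6.0 has a rule beginning "If performed for research purposes, the results of the", which covers reporting of a research FDG scan to the medical record.
- Section 6.2 begins "If performed for research purposes, subjects will undergo standard oncologic" and goes on to the FDG imaging procedure.
- Section 6.6 lists FDG and FFNP risks together, and says: "Patients will be scanned on 2 separate occasions with FFNP plus one FDG scan resulting in a total exposure of 4.28 rem".

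**The concern.** Section 8.0 gives one reason for not recording FDG adverse events, and it is true of only some of the scans. Where FDG is done because the study needs it, for example for the heterogeneity comparison in objective 2.2.1, the injection is an exposure caused by the research. Staff who follow Section 8.0 to the letter would leave events after that injection out of the case report forms.

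What is at stake is the completeness of the safety record. Section 8.7 requires all adverse events, whatever their grade or attribution, to go into the data and safety monitoring report, but that report can hold only what was recorded. Sections 8.0 and 8.7 therefore pull in different directions for a research FDG scan.

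**Working it through.** **1. Is FDG a study exposure by the protocol's own account?** Section 6.6 gives 1.51 rem for FDG with its CT and 1.39 rem for each FFNP scan with its CT.

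- With FDG: 1.51 + 2 × 1.39 = 4.29 rem, against the stated 4.28 (a difference of 0.01, consistent with rounding).
- Without FDG: 2 × 1.39 = 2.78 rem.

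The stated total is reached only if FDG is counted.

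**2. Does another section pick up FDG events?** Set side by side:

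- Section 8.0, monitoring: applies during imaging and is not limited by tracer. An event may be seen.
- Section 8.0, recording: waived for FDG without distinguishing research from standard care.
- Section 8.0, reporting windows: start from FFNP or estradiol only.
- Section 8.1, definition: names FFNP and estradiol only. It describes the subject and does not expressly exclude an FDG event in such a subject, but it does not bring one in either.
- Section 6.9, contact: says that "following injection, a follow-up telephone call will be made to the patient", without naming the tracer. Section 8.0 and note 2 of the study calendar tie this follow-up to FFNP.
- Study calendar, note 4: FDG must be on a different day from FFNP, preferably earlier. The FFNP contact is thus not designed to cover FDG.
- Sections 8.2, 8.6 and 8.7: unanticipated problems related to research procedures, and reportable deaths, have a route whichever tracer was given.

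What is left uncovered is the ordinary adverse event after a research FDG injection, which has no recording and no planned follow-up.

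**3. How large can it be?** A patient with a research FDG scan has 1 FDG and 2 FFNP injections, so the ceiling is 1/(1 + 2) = 33% of that patient's study tracer injections. Let f be the proportion of patients with a research FDG scan, which the documents do not give. Across the study, the share of study tracer injections is f/(2 + f):

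- f = 0: 0%
- f = 0.5 (assumed for illustration): 0.5/2.5 = 20%
- f = 1: 1/3 = 33%

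With 50 patients, that is 0 to 50 FDG injections beside 100 FFNP injections. These are counts of injections, not shares of risk or of events.

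**4. A related, smaller point on FFNP.** The contact range is 24 − 6 = 18 hours to 24 + 6 = 30 hours, and the reporting window is 24 hours. A contact at the earliest permitted time precedes the end of the window by 24 − 18 = 6 hours, or 6/24 = 25%. This is the worst case for one contact; a contact at or after 24 hours leaves nothing uncovered.

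**The case against.** The best defence is that reduced collection for FDG may be deliberate. FDG is supplied under the facility's ANDA, dosed by the standard nuclear medicine protocol, and reported like a routine examination even when done for research. On that view Section 8.0 means that FDG follows standard procedures, and safety effort is rightly concentrated on FFNP and the estradiol challenge. It is a reasonable position, and it supports a lighter regime for FDG. It does not rescue the reason given: a scan done by routine technique but ordered for the study is still a research procedure.

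The defence also limits the point. A reader might infer any of the following, and the documents support none of them:

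- *Events after research FDG go wholly unseen or unreported.* In-session monitoring remains, and unanticipated problems and reportable deaths are still reported.
- *A third of the safety information is lost.* The 33% is a per-patient ceiling on injections. Section 5.2 lets a recent FDG scan, bone scan or contrast CT stand in for the study scan, so some patients may have no research FDG at all.
- *FDG is a known hazard here.* Section 6.6 does say that "such a reaction could be serious and may result in death", but under the rare risks, and the same sentence states that no such reaction has been reported to date with either tracer.
- *FFNP safety reporting closes at the contact.* Nothing says so. An event within 24 hours is reportable whenever it is learned of, and 24 ± 6 hours is a tolerance centred on 24. Moving the window to 24 to 30 hours would close the small gap in active questioning but halve the scheduling range, from 12 hours to 6. That is a trade-off, not a correction.

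**Conclusion.** The point holds as an inconsistency in the safety sections. Section 8.0 applies a standard-of-care reason to all FDG scans, while Sections 5.2, 6.0, 6.2 and 6.6 provide for research FDG, and Section 8.1 does not fill the gap. Its effect is confined to recording and follow-up of ordinary adverse events in patients who have a research FDG scan: one of three tracer injections at most in such a patient, and between 0 and 33% of study tracer injections overall, depending on a proportion the documents do not state.

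This rests on reading Section 8.0 literally, as site staff would. The primary endpoints, the power calculation and the analyses in Section 10.1 are unaffected. It is a minor point, worth correcting because the wording is plainly at odds with other sections and the repair is cheap. The timing of the FFNP contact is secondary and would not merit a change by itself.

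**What to change.** - In Section 8.0, limit the waiver to FDG scans done as standard of care.
- For research FDG, record adverse events seen during the session or volunteered later. The PET imaging form, already due at each imaging session under Section 7.1, could carry them.
- Add research FDG to the definition in Section 8.1 and to the 24-hour reporting window in Section 8.0.
- A follow-up call after research FDG is optional. If none is planned, say so and give a reason that holds for research scans.
- Optional, for FFNP: when the contact is made before 24 hours, note on the form that events up to 24 hours remain reportable and ask the patient to report them. This keeps the present scheduling range.

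The cost is a protocol amendment and a few lines of recording for each research FDG scan, for at most 50 sessions if every one of the 50 patients had one. An optional call would add one short contact per such patient.

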5.3 Estradiol Challenge Test

The estradiol challenge test will consist of administering a total of 6 mg of estradiol dosed orally as three 2 mg tablets with each tablet being administered approximately 8 hours apart and within a 24 hour period. This estradiol medication will be provided to the patient by the study. Dosing will be such that the third dose of estradiol will be administered at a minimum 8 hours (8 ± 2 hours) and a maximum 48 hours prior to the scheduled injection of ^{18}F -FFNP for the repeat ^{18}F -FFNP-PET/CT imaging session. Timing of the estradiol administration is critical so that the effect of estradiol will be captured within the imaging session. The first dose of estradiol can be administered as soon as immediately following the baseline ^{18}F -FFNP-PET/CT imaging session with the post estradiol ^{18}F -FFNP -PET/CT imaging session being scheduled for the following day. No more than a maximum of 4 weeks should occur between the baseline and the post estradiol challenge ^{18}F -FFNP -PET/CT imaging sessions. A subject specific calendar will be given to each participant that includes dates and times for estradiol administration and follow up ^{18}F -FFNP-PET/CT imaging session. Whenever possible, blood will be obtained for measurement of the serum estradiol level, using a high-sensitivity radioimmunoassay (Herting MM. BJ. Cereb Cortex. 2012 Sep;22(9):1979-92) before injection of ^{18}F -FFNP at the baseline and after estradiol challenge before the 2nd ^{18}F -FFNP injection to document that it increased appropriately.

5.4 Risks Related to Estradiol Challenge Test.

Side effects from taking a total 6 mg of estradiol over a 24 hour period are expected to be minimal. Subjects may experience nausea from a dose this small. When estradiol is administered in much higher doses as therapy and given daily over a longer period of time the following side effects have been reported: nausea and or vomiting; bone pain, breast tenderness and/or enlargement; vaginal bleeding, tiredness, changes in skin color; insomnia (difficulty falling or staying asleep); yeast infections, increase or decrease in vaginal secretions, and headaches

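### The section 8.0 estradiol reporting window runs 24 hours from the first of three doses, so it can close before the FFNP window reopens and conflicts with sections that set no hour limit

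*Combined protocol and SAP*

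**What the plan says.** Section 8.0 sets two reporting windows for events judged related or possibly related to the research. One is the 24 hours after FFNP administration. The other covers events "within 24 hours of the first dose of estradiol which are graded related or possibly related to participation in the research will be reported". The same section places a contact 24 ± 6 hours after FFNP injection "to assess for adverse events as related to" the FFNP injection or the PET/CT imaging; estradiol is not named there.

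Section 5.3 describes three tablets, "each tablet being administered approximately 8 hours apart and within a 24 hour period". The third is taken at least 8 (± 2) hours and "a maximum 48 hours prior to the scheduled injection of" FFNP for the repeat scan. Dosing may start right after the baseline scan, with the repeat "imaging session being scheduled for the following day", but later starts are allowed: "No more than a maximum of 4 weeks should occur between the baseline and the post estradiol challenge" scans. Section 5.2 describes the repeat scan as "a second one immediately following one day of estradiol challenge test", and adds that "any subject who does not complete both FFNP-PET/CT imaging sessions for any reason may be replaced on study".

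Other sections are wider. Section 6.9 words the follow-up call as a general adverse-event check. Section 8.1 counts events in anyone given FFNP, research estradiol or both, and sets no number of hours. Section 8.7 sends all adverse events, whatever their grade or attribution, to the cumulative DSM report. Section 9.0 provides for ongoing monitoring of serious toxicities and for reporting adverse events once the study team knows of them.

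**The concern.** Estradiol is given here only for research. Its reporting clock starts at the first of three doses and takes no account of the other two, and no section gives a reason for this. Cover under section 8.0 resumes only at the second FFNP injection. Whether that section makes a related event after the last dose reportable can therefore depend on when the scan is booked.

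At stake is consistent capture of related events, chiefly expected and non-serious ones. Unanticipated-problem reporting (8.2, 8.6) requires an unexpected event, so it would not normally take in something like the nausea that section 5.4 mentions.

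A second problem concerns the subject who takes estradiol and never has the second injection. That subject has no second FFNP window and no contact after it.

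**Working it through.** The plan states no length for the interval between the two windows, so there is no figure to reproduce. The check is timeline arithmetic, with the first estradiol dose at hour 0.

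**Inputs**
- Estradiol window: hours 0 to 24 (8.0).
- FFNP window: 24 hours from each injection (8.0).
- Third dose at hour t3. Assumed nominal schedule: 0, 8 and 16, so t3 = 16. Outer limit: t3 = 24, if the doses fill the whole 24-hour period (5.3). The outer limit means about 12-hour spacing, which strains the stated spacing of about 8 hours.
- Lag L from third dose to second injection: 6 hours (8 − 2) to 48 hours (5.3).

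**Formula.** The second injection is at hour t3 + L. Time in neither window before it = max(0, t3 + L − 24). On the nominal schedule this is max(0, L − 8).

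| L (h) | Injection, t3 = 16 | Gap (h) | Injection, t3 = 24 | Gap (h) |
|---|---|---|---|---|
| 6 | hour 22 | 0 (windows overlap by 2) | hour 30 | 6 |
| 8 | hour 24 | 0 | hour 32 | 8 |
| 24 | hour 40 | 16 | hour 48 | 24 |
| 48 | hour 64 | 40 (hours 24–64) | hour 72 | 48 (hours 24–72) |

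The estradiol window outlasts the third dose by 24 − 16 = 8 hours on the nominal schedule and by 24 − 24 = 0 hours at the outer limit.

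**Can the baseline FFNP window fill the gap?** No. The baseline injection precedes the first dose, so its 24 hours end before hour 24.

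**Scheduled contacts**
- The baseline contact comes at most 24 + 6 = 30 hours after the baseline injection, hence before hour 30. If estradiol starts later within the 4 weeks, that contact comes before any dose.
- The contact after the second scan falls 18 to 30 hours after that injection. On the nominal schedule with L = 48 this is hour 64 + 18 = 82 to 64 + 30 = 94, after the whole gap has passed.
- A subject dosed but not rescanned has only the baseline contact.

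**The case against.** The strongest reply is that the uncovered hours exist only if section 8.0 is read alone. Section 8.1 has no hour limit. The expedited adverse-event row in 8.7 refers to 8.1 and 8.2 rather than to the 8.0 windows, and its cumulative row takes in everything. Section 9.0 has adverse events reported once known. Rescanned subjects are seen in person at the second scan and contacted a day later, in general terms according to 6.9. Sections 5.4 and 6.7 expect little or no toxicity from the challenge.

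Most of this stands, and it limits the point to a minor one. It does not remove it. Section 8.0 says its in-window events are reported under the guidelines that follow it, so whether its limit also governs 8.7 is unclear. Section 9.0 depends on the team learning of the event, which is weakest for a subject not rescanned.

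Three stronger readings are tempting and are not supported:
- *Events in the gap go unreported.* Sections 8.1, 8.7 and 9.0 leave routes open for events that become known.
- *Nobody asks about estradiol effects.* The narrow contact wording in 8.0 conflicts with 6.9 and 8.1; it does not show that the question is not asked.
- *Forty hours is the maximum, or next-day scanning leaves almost no gap.* Forty hours belongs to the nominal schedule, and dose spacing is only approximate. Section 5.3 attaches ± 2 hours to the minimum lag and gives no clock time for a next-day scan, so no gap can be fixed for that case.

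**Conclusion.** The point holds as a minor one: a stated rule that works badly and is cheap to improve. On the assumed schedule of doses at hours 0, 8 and 16, the two section 8.0 windows fail to meet whenever the second injection comes more than 8 hours after the last dose. The uncovered time is L − 8 hours, reaching 40 at the permitted 48-hour lag, or 48 if dosing fills the full 24 hours.

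The consequence is twofold: section 8.0 disagrees with 8.1, 8.7 and 9.0 about what is reportable, and a subject dosed but not rescanned has no scheduled post-scan contact. The documents give no event rates or onset times after the challenge and no frequency of incomplete imaging, so the number of events affected cannot be computed. The primary analysis, which compares FFNP uptake change between responders and non-responders, is unaffected.

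**What to change.** - In section 8.0, run the estradiol reporting window without a break from the first dose through the existing 24 ± 6 hour contact after the second FFNP injection.
- For a subject dosed but not rescanned, state a closing time counted from the last estradiol dose and require a contact.
- Name estradiol-related events in the section 8.0 contact.
- Reconcile 8.0 with 5.3, 6.9, 8.1, 8.7 and 9.0, and say whether the 8.0 time limit applies to the 8.7 rows.

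The gain is removal of the L − 8 uncovered hours on the nominal schedule, and a defined contact for subjects who leave before the second scan. The end of the window would still move with the scan date, but no permitted schedule would leave a hole between the first dose and that contact. No dose, scan time or clinical rule changes. The cost is short wording edits, one CRF question at a contact that already takes place, an occasional extra call and slightly more events recorded.
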